#### **Pharmaceutical Form**

TS23 drug product is a liquid for IV administration. Each vial contains 10 mL of a 10.0 mg/mL solution of TS23 in a phosphate buffer-based formulation.

#### **Dosage and Administration**

TS23 will be administered as a ~15-minute IV infusion at the dose stipulated in study protocols. In the phase 1 study (TS CP01-2015) in healthy participants, TS23 was administered as single IV infusion dose ranging from 2.5 mg/kg to 10.0 mg/kg.

---

## **Special Populations**

TS23 has not yet been tested in children, adults over 60 years of age, or participants with renal or hepatic impairment.

## **Contraindications**

TS23 is contraindicated for participants with clinically significant active bleeding or for participants with known hypersensitivities to the drug substance (monoclonal antibodies) or to inactive ingredients in the formulation (such as sodium phosphate or sorbitol).

## **Warnings and Precautions**

**Bleeding:** Due to the mechanism of action of TS23 on fibrinolysis, bleeding is a potential risk. Humans with  $\alpha$ 2AP deficiency have normal coagulation and platelet function. However, after coagulation, they may experience blood oozing from sites of external or internal injury. Because of the limited clinical data available with TS23, the potential for clinically significant or major bleeding in participants receiving DS- 9231 cannot be excluded. Participants should be carefully monitored for any signs of bleeding and treated appropriately. Antifibrinolytic agents such as epsilon amino caproic acid (Amicar) or tranexamic acid (Lysteda) should be considered if clinically indicated and used according to the package inserts.

No infusion-related or allergic reactions with TS23 have been observed in the only study in humans to date and the risk to participants remains unknown. Due to limited clinical experience, TS23 should be administered in clinical settings with access to resuscitation facilities and under the supervision of appropriately trained personnel. If severe allergic reactions occur, administration of TS23 should be immediately discontinued and the subject appropriately treated as per local guidelines.

## **Interactions**

No data in humans available to date.

## **Pregnancy and Lactation**

TS23 has not been studied in women and its potential effects on the fetus are unknown. Until conclusive studies have been conducted, TS23 should not be administered to pregnant women or women attempting to conceive, and adults of reproductive potential must adhere to contraception guidelines specified in the study protocols. No studies have been conducted to evaluate the potential of TS23 to be excreted in human breast milk. TS23 should not be administered to women who are breastfeeding or plan to breastfeed within 3 months.

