## **5.2 Exclusion Criteria**

1. Plan to receive endovascular treatment.
  2. Received or plan to receive IV thrombolysis.
  3. Pre-stroke modified Rankin score >2.
  4. Previous treatment with TS23 or known previous allergy to antibody therapy.
  5. Known pregnancy, women who are breastfeeding or plan to breastfeed within 3 months of receiving TS23 or have a positive urine or serum pregnancy test for women of childbearing potential.
  6. Known previous stroke in the past 90 days.
  7. Known previous intracranial hemorrhage, intracranial neoplasm, subarachnoid hemorrhage, or arterial venous malformation.
  8. Known active diagnosis of intracranial neoplasm.
  9. Clinical presentation suggestive of a subarachnoid hemorrhage, even if initial CT scan was normal.
  10. Surgery or biopsy of parenchymal organ in the past 30 days.
  11. Known trauma with internal injuries or persistent ulcerative wounds in the past 30 days.
  12. Severe head trauma in the past 90 days.
  13. Persistent systolic blood pressure >180mmHg or diastolic blood pressure >105mmHg despite best medical management.
  14. Serious systemic hemorrhage in the past 30 days.
  15. Known hereditary or acquired hemorrhagic diathesis, coagulation factor deficiency, or oral anticoagulant therapy with International Normalized Ratio (INR) >1.7.
-

16. Platelets <100,000/mm^3.
17. Hematocrit <25 %.
18. Elevated aPTT above laboratory upper limit of normal.
19. Creatinine > 4 mg/dl, or patients receiving renal dialysis, regardless of creatinine.
20. Received heparin or low molecular weight heparins (such as Dalteparin, Enoxaparin, Tinzaparin) in full therapeutic dose within the previous 24 hours.
21. Received Factor Xa inhibitors (such as Fondaparinaux, apixaban or rivaroxaban) within the past 48 hours.
22. Received direct thrombin inhibitors (e.g., argatroban, dabigatran, bivalirudin, desirudin, lepirudin) within 48 hours.
23. Received glycoprotein IIb/IIIa inhibitors within the past 14 days.
24. Known pre-existing neurological or psychiatric disease, which would confound the neurological/functional evaluations.
25. Current participation in another research drug treatment protocol (i.e., participants could not start another experimental agent until after 90 days).
26. Concurrent acute myocardial infarction, pulmonary embolism, deep venous thrombosis, or other thrombotic event that requires anticoagulation or anti-platelet treatment.

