### **5.4 Strategies for Recruitment and Retention**

The target sample size for SISTER trial is 300 participants in the mITT population enrolled over 36 months at 50 active sites at a given time (average accrual rate of 2.6 patient per site per year). All 50 active sites participating in the trial will screen and enroll consecutive patients who meet the trial criteria. The study personnel will not discriminate based on age, gender, race/ethnicity. Participants will be screened and enrolled in the emergency room of all participating comprehensive stroke centers.

---

The study personnel will work with local treatment teams to identify potential participants. The strategies of such identification will be outlined in the Manual of Procedures document as well as local site-level Standard Operating Procedures (SOPs) document.

By the nature of the condition, a considerable portion of patients with acute ischemic stroke may experience acute cognitive dysfunction. They are a vulnerable population. Inclusion of these patients is required to optimally inform safety and efficacy profile of the study drug for all acute stroke patients that meet the study criteria and to generate results that are generalizable. Exclusion of all patients with cognitive impairment at the time of enrollment will result in a study population that is not representative of AIS patients presenting within the 4.5-24-hour time window. Our team has extensive experience in undertaking investigations that involve vulnerable patients, and we will apply our expertise in minimizing risks for these study participants. Our study team has extensive experience with surrogate consent process as well. Because SISTER is a phase 2 trial testing safety of a novel drug, we will exclude pregnant women due to potentially unknown risks of the medication. Other special populations, such as fetuses, neonates, prisoners, and children, will not be eligible for inclusion.

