### **6.2.2 Formulation, Appearance, Packaging, and Labeling**

The investigational product TS23 is manufactured under the direction of Translational Sciences, Inc. by Cytovance Biologics, Inc. TS23 is supplied in 10 ml stoppered vials that will be labeled as an investigational drug with appropriate study identifiers to permit tracking of vials. Each vial contains 10 mL of a 10 mg/mL solution of TS23 in a phosphate buffer-based formulation (10 mM sodium phosphate, 50 mM sodium chloride, 5% Sorbitol, pH 6.0). It appears as a clear liquid, virtually free of particles.

Details of the packaging and labeling of TS23 10 mL of 10 mg/mL solution for infusion and matching placebo will be provided in the pharmacy instructions.

Packaging and labeling will be performed according to GMP.

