## 8.1 Baseline

Patients presenting with acute ischemic stroke will be evaluated by a stroke team physician, in accordance with institutional practice, to establish study eligibility. All consecutive patients meeting study entry criteria will be enrolled in the trial.

Participants enrolled in SISTER should not receive antithrombotics for at least 24 hours after study drug administration.

The study order sets will specifically include an order not to administer antithrombotics within the first 24 hours after study drug administration. This will also be closely monitored as participants will be admitted to the intensive care unit setting for at least first 24 hours after drug admission.

The following data will be documented at the baseline evaluation for randomized patients:

- Demographics: Age, sex, race/ethnicity
  - Medical history regarding presence of concomitant medical conditions (e.g. hypertension, diabetes, hyperlipidemia, atrial fibrillation, prior ischemic stroke, prior hemorrhagic stroke, current or past smoking)
  - Vital signs: Systolic and diastolic arterial blood pressure; heart rate, temperature
  - Concomitant medications at time of stroke onset (anticoagulation, antiplatelets, antihypertensives, statins, antidiabetics, cholesterol reducers)
  - Pre-stroke functional state: pre-stroke modified Rankin Scale, pre-stroke ambulatory status (independent, with assistance, unable)
  - Laboratory Evaluation
    - Measurement within 12 hours prior to study drug administration (if there are multiple measurements, then consider the latest measurement)
      - SOC: aPTT, PT with INR, CBC, platelet count.
    - First measurements upon presentation to study hospital, within 2-3 hours of study drug administration):
      - SOC: Glucose, creatinine
    - First value collected during hospitalization:
      - SOC: Hemoglobin A1C, Lipid Panel containing total cholesterol, HDL, LDL & triglyceride.
  - Neurologic Deficit: NIHSS upon arrival to the study hospital
-

- Brain and Vascular imaging at presentation:
    - CT or MRI
    - CTA or MR angiography (MRA)
    - CTP or MRI-PWI, if applicable per institutional practices
  - Initial Workflow Time Metrics: Date and time of:
    - Last known well (LKW)
    - Symptoms first observed (SFO)
    - Outside hospital (OSH) date/times (if patient first presented to an OSH):
      - Arrival at OSH (“Door-In”)
      - Departure from OSH (“Door-Out”)
    - Study Hospital date/times:
      - Arrival at Study Hospital

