#### **11.1.9 Protocol Deviations**

A protocol deviation is any noncompliance with the clinical trial protocol, ICH GCP, or MOP requirements. The noncompliance may be either on the part of the participant, the investigator, or the study site staff. As a result of deviations, corrective actions are to be developed by the site and implemented promptly.

These practices are consistent with ICH GCP:

- 4.5 Compliance with Protocol, sections 4.5.1, 4.5.2, and 4.5.3
- 5.1 Quality Assurance and Quality Control, section 5.1.1
- 5.20 Noncompliance, sections 5.20.1, and 5.20.2.

It is the responsibility of the site investigator to use continuous vigilance to identify and report deviations within 15 working days of identification of the protocol deviation. All deviations must be addressed in study source documents, reported to NINDS Program Official and NIDMC. Protocol deviations must be sent to the reviewing IRB per their policies. The site investigator is responsible for knowing and adhering to the reviewing IRB requirements. Further details about the handling of protocol deviations will be included in the MOP.

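### Exclusions 4 and 5 leave out two groups that section 6.1.1 says should not receive TS23: patients hypersensitive to its inactive ingredients and women attempting to conceive

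*Protocol*

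**What the plan says.** The product text in Protocol section 6.1.1 sets two kinds of restriction that matter here. Under Contraindications, TS23 is ruled out for known hypersensitivity to monoclonal antibodies and also "to inactive ingredients in the formulation (such as sodium phosphate or sorbitol" are the examples given). Under Pregnancy and Lactation, it states that "TS23 should not be administered to pregnant women or women attempting to conceive", and it says the same of women who are breastfeeding or plan to within 3 months. Section 6.2.2 gives the formulation as "10 mM sodium phosphate, 50 mM sodium chloride, 5% Sorbitol, pH 6.0", so both named excipients are in every vial.

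The matching entries in section 5.2 are exclusion 4, "Previous treatment with TS23 or known previous allergy to antibody therapy", and exclusion 5, which covers known pregnancy and "women who are breastfeeding or plan to breastfeed within 3 months of receiving TS23 or have a positive urine or serum pregnancy test" (the test applying to women of childbearing potential).

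On enrollment, section 5.4 says "All 50 active sites participating in the trial will screen and enroll consecutive patients who meet the trial criteria", and section 8.1 says "All consecutive patients meeting study entry criteria will be enrolled in the trial".

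**The concern.** The eligibility list decides who is randomized. When a protocol names a group that should not be dosed, that group normally appears among the exclusions, so that screening stops the patient before allocation. Here two named groups do not appear. Following sections 5.1 and 5.2 to the letter, a site could randomize a patient with known sorbitol hypersensitivity, or a woman trying to become pregnant, and learn of the bar only on turning to section 6.1.1.

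What is at stake is participant protection. Section 6.1.1 itself says that the risk of infusion or allergic reactions is unknown, that TS23 has not been studied in women, and that its effects on a fetus are unknown. Screening is also done under time pressure: inclusion 6 requires dosing within 90 minutes of the qualifying perfusion scan, and section 5.4 expects that many patients will be cognitively impaired and that surrogates will consent. In that setting the numbered criteria are the practical safeguard.

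**Working it through.** There is no figure to reproduce. The check sets the restrictions in 6.1.1 beside the entry criteria.

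**Step 1: group by group.**

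| Group named in 6.1.1 | Subsection of 6.1.1 | Strength of wording | Match in 5.2 |
|---|---|---|---|
| Hypersensitive to monoclonal antibodies | Contraindications | contraindicated | exclusion 4 |
| Hypersensitive to inactive ingredients | Contraindications | contraindicated | none |
| Pregnant | Pregnancy and Lactation | should not | exclusion 5 |
| Attempting to conceive | Pregnancy and Lactation | should not | none |
| Breastfeeding | Pregnancy and Lactation | should not | exclusion 5 |
| Planning to breastfeed within 3 months | Pregnancy and Lactation | should not | exclusion 5 |

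Groups compared: 6. Matched: 4. Unmatched: 6 − 4 = 2. The Contraindications text also bars active bleeding. The bleeding-related exclusions are a separate matter and are not counted here.

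**Step 2: could another criterion catch them?** There are 7 inclusion and 26 exclusion criteria, 7 + 26 = 33 in all. None names either group. The nearest candidates do not do the job:

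- Inclusions 5 and 6 speak of being able to receive the drug, but only within a time limit.
- Exclusion 4 is about antibody allergy. A patient whose known reaction is to sorbitol, and who has never had an antibody, is outside it.
- The pregnancy test in exclusion 5 detects pregnancy, not an attempt to conceive. Planned breastfeeding within 3 months is a different condition: a woman not yet pregnant would not ordinarily meet it.

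**Step 3: could another section close the gap?** Section 5.4 mentions pregnant women but not women attempting to conceive. Section 9.3.8 governs the reporting of pregnancies after dosing. Section 6.1.1 refers to contraception guidelines in the study protocols, but this protocol contains none.

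**Step 4: what happens to such a patient.** They satisfy 5.1 and 5.2, and the consecutive-enrollment text in 5.4 and 8.1 points to enrolling them. After randomization there are two paths:

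- The site notices 6.1.1 and withholds the drug. The participant is then randomized but undosed, may be replaced under 7.2, and is outside the modified intent-to-treat population (5.3, 10.4).
- The site does not notice, and the patient is dosed against 6.1.1. Section 11.1.9 would make this a deviation: "A protocol deviation is any noncompliance with the clinical trial protocol, ICH GCP, or MOP requirements".

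**Step 5: excipient exposure.** Table 2 doses run from 180 to 1000 mg. At 10 mg/mL this is 180/10 = 18 mL to 1000/10 = 100 mL of product before dilution. If 5% sorbitol means weight per volume (an assumption; the protocol does not say), that is 18 × 0.05 = 0.9 g to 100 × 0.05 = 5 g given intravenously over about 15 minutes. Placebo is saline alone, so only the active arms carry this exposure.

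**The case against.** The strongest reply is that the bar is already in the protocol. Section 6.1.1 belongs to the same document as section 5.2, no text tells a site to dose either group, and a recognized case ends in a withheld dose and possible replacement. Exposure needs a site to overlook 6.1.1. This stands, and it limits the point to an incomplete carry-over. It does not remove it, because a bar found only in the product description leaves the patient eligible for randomization.

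It can also be said that the Pregnancy and Lactation wording is the softer *should not*. That is right, and it should not be restated as an absolute prohibition; only the excipient bar is called a contraindication. But the same softer wording covers pregnancy and breastfeeding, which were made exclusions, so it does not explain why attempting to conceive was left out.

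The text in 6.1.1 may be general product language: it speaks of study protocols in the plural and still carries a different compound code. That is plausible, and it makes the missing contraception guidance look like an unedited cross-reference. Other safeguards also reduce the risk: pregnancy is excluded by history and test, dosing takes place with resuscitation facilities at hand, and patients are watched in a high-acuity setting for at least 4 hours.

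Two further inferences are tempting and are not supported:

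- A reader might conclude that a wrongly dosed patient would stay in the Per-Protocol sample because no listed criterion was breached. Section 10.4 removes eligibility violations, with enrollment in error as its example, and does not confine these to numbered criteria. The patient's status is therefore open.
- A reader might take the absence of a pregnancy test from the laboratory list in 8.1 as a gap. That list records data to be documented for randomized patients and includes values obtained later in the hospital stay. Exclusion 5 already names the test.

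**Conclusion.** The mismatch is real: two of the six allergy or reproductive groups that 6.1.1 says should not receive TS23 have no matching entry criterion, and no other section supplies one. A patient in either group can be randomized as the criteria stand. This does not amount to permission to treat.

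The effect is small in numbers. Few participants are likely to belong to either group in this stroke population; the protocol gives no rate, so that is a judgment. The count of two in six describes the carry-over and does not measure risk. Neither the primary analysis nor any inference from it is affected.

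The conclusion assumes that sites screen mainly from 5.1 and 5.2, and that the eligibility form follows those lists. The form and the Manual of Procedures are not among the documents. If they already contain both items, the practical gap is closed, though the protocol text would still need to agree with itself. The correction is worth making because it costs almost nothing and places the stop before randomization.

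**What to change.** In section 5.2:

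- Extend exclusion 4 with: *or known hypersensitivity to any component of the formulation, including sorbitol and sodium phosphate*.
- Extend exclusion 5 with: *or known to be attempting to conceive*. The word *known* keeps the criterion workable when the patient cannot answer and a representative may not know.

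Add the two matching items to the eligibility form. As optional tidying, either state the contraception requirement in the protocol or delete the reference to it in 6.1.1.

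The cost is two phrases and two form items, plus one sentence if the optional change is made. These can go into the next amendment, with the usual IRB review. Sample size, randomization and analysis are unchanged.

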## **Adverse Reactions or Undesirable Effects**

TS23 will augment fibrinolysis and, similar to other thrombolytic agents, bleeding will be the most commonly anticipated AE. The bleeding events observed in the phase 1 human volunteer study were minor in nature, were transient and clinically inconsequential, did not require medical intervention, and were categorized as grade 1 events. Currently, there are no data available in such patients with active

---

illnesses who also may receive concomitant antithrombotic therapy. In pre-clinical studies, a surrogate a2AP-I for TS23 did not increase surgical bleeding in mice when used in combination with rivaroxaban, low molecular weight heparin or aspirin, by comparison to these agents alone (see [Investigator's Brochure](#)). However, in patients receiving concomitant antithrombotic therapy, the risk of bleeding may be higher. In case of severe bleeding requiring therapy, appropriate medical and surgical treatment should be instituted and antifibrinolytic agents such as epsilon amino caproic acid (Amicar) or tranexamic acid (Lysteda) may be considered, if clinically indicated, and used according to the package inserts (see Overdose, below).

TS23 is a chimeric monoclonal antibody and consequently a rare possibility of immunogenic response or infusion reaction exists. No infusion reactions were observed in the phase 1 human volunteer study. Furthermore, such reactions usually are expected when a subject receives a second or repeat dose of such therapy.

Clinical data from the only study with TS23 to date has not indicated any significant safety concerns, with a low number of treatment emergent adverse events (TEAEs) and no trends in the nature and/or severity of TEAEs detected. No deaths or treatment-related SAE have occurred in the development program. Observed bleeding TEAEs have been associated with venipuncture and have been of mild severity.

### **Reference Safety Information/Adverse Reactions**

Based on the review of the available clinical data, currently there are no adverse reactions considered expected for TS23. All AEs are considered unexpected for regulatory reporting purposes.

### **Previous Clinical Experience with Products of the Same Class**

No information about previous experience with products of the same class is available at this time.

### **Overdose**

All attempts will be made to minimize overdosing by providing a simple dosing table to all sites ([Table 2](#)). There is currently no information available regarding potential overdose of TS23. In case of suspected overdose, participants should be closely monitored in an inpatient, supervised setting. Supportive care measures should be initiated as determined by the investigator's judgment. Due to the known mechanism of action of TS23, AEs events associated with TS23 overdose are likely to be related to increased fibrinolysis. In such cases, antifibrinolytic agents such as epsilon amino caproic acid (Amicar) or tranexamic acid (Lysteda) should be considered if clinically indicated and used according to the package inserts.

